1.2 Aim

The aim of this study is to determine the sensitivity and specificity of magnetic resonance enterography (MRE) as a screening tool for axial spondyloarthritis (axSpA) in a cohort of adult patients with Crohn's disease (CD) in a secondary-care hospital, using dedicated axial magnetic resonance imaging (MRI) with clinical assessment as the gold standard.

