2.1 Background and rationale for the proposed study

Spondyloarthritis (SpA) is a term used to describe a group of chronic inflammatory musculoskeletal diseases that can present with axial and / or peripheral joint disease. SpA encompasses non-radiographic axial spondyloarthritis (nr-axSpA), AS and psoriatic arthritis (PsA). The prevalence of SpA has been estimated to range between 0.01% (Japan) and 2.5% (Alaska and Russia) of the general population [1]. There is an association with the Human Leucocyte Antigen B27 (*HLA-B27*) which is estimated to be present in 50-95% of patients with SpA [2]. Patients with SpA have an excess burden of inflammatory bowel disease (IBD), which primarily includes CD and ulcerative colitis (UC). It is estimated that up to 40% of patients with PsA also have axial disease (PsSpA) [3]. The estimated prevalence of diagnosed IBD in patients with PsSpA is 12% and in patients with AS is 10% [3]. However, few studies have investigated the presence of undiagnosed SpA in patients with IBD. SpA can have a significant negative impact on various aspects of quality of life including employment, social life and sexual relations [4-6]. PsA has been found to be associated with relatively high levels of unemployment (20%-50%) with some improvement following conventional or biologic disease modifying anti-rheumatic drugs (DMARDs) [7, 8]. Timely diagnosis and treatment is therefore potentially crucial.

Novel biologic therapies for SpA have been developed to target the dysregulated innate and adaptive immune systems which underpin its pathophysiological and inflammatory processes. Such targets include pathways involving the cytokines interleukin (IL)-17, IL12/23 and tumour necrosis factor (TNF). These cytokine pathways are also common to the pathophysiological processes of IBD [9-12]. There have subsequently been a number of biological therapies that have emerged over the last decade with a license to treat IBD and SpA, including anti-tumour necrosis factor (anti-TNF), anti-IL-23 and anti-IL 17 agents. Whilst these treatments are not equally efficacious for both conditions, if used appropriately and early in the course of the disease, they can have a significant impact on the burden of disease [13, 14].

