4.3 ProSpA-CD-Assess phase

4.3.1 Assessment of patients with lesions on MRE consistent with axSpA (cases)

Patients with lesions on MRE consistent with axSpA (and no known diagnosis of SpA) will be informed by telephone and letter by the gastroenterology team and referred to [name] NHS rheumatology SpA clinic. They will also be sent separately an invitation letter, participant information sheet (PIS) and reply slip (study interest form with a stamped-addressed envelope for returns) for the ProSpA-CD-Assess phase of the study by the gastroenterology team. CD subjects with a known diagnosis of SpA who are already under review by rheumatology and who have lesions on MRE consistent with axSpA will also be considered as cases and will be sent an invitation letter, PIS and study interest form. However, they will instead be invited to attend the rheumatology SpA research clinic to be assessed for axSpA (with the control group) as this will be considered to be outside of their routine NHS care.

In the NHS SpA clinic, the patients will be assessed by a single rheumatologist ([name], in a supernumerary capacity with salary funded by the research grant) for clinical evidence of axSpA *as per* standard of care using the 2009 ASAS criteria for axSpA, modified New York criteria for AS and CASPAR criteria for PsA (see Appendices 5, 6 & 7). The assessment will include a clinical history, examination (including BASMI, 68 tender joint count, 66 swollen joint count, the SPARCC enthesitis index and for skin or nail psoriasis), PROMs (BASDAI, BASFI, VASbp, ASDAS and HAQ-DI), blood samples (FBC, renal function, LFTs, CRP and ESR unless performed in the preceding month, and HLA-B27 unless previously performed) and stool samples (the monitoring of IBD luminal activity with faecal calprotectin is well established [41, 42]; stool samples will therefore also be collected to measure faecal calprotectin concentrations unless performed in the preceding month). During the consultation, the ProSpA-CD-Assess phase of the study will also be discussed further and patients will be provided with the opportunity to ask any questions they may have regarding the study. If they agree to participate in the study and meet the inclusion criteria, then written informed consent will be taken. The blood and stool tests will be performed as per standard of care if clinically indicated or for research and funded by the research grant if not clinically indicated.

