4.3.2 Assessment of subjects with no lesions on MRE consistent with axSpA (controls)

Subjects (including those with a known diagnosis of SpA) who have consented to having their MRE scans reviewed, but who do not have lesions consistent with axSpA, will be informed in writing of this by the gastroenterology team. They will also be advised that they may be invited to enter the study as a control subject if they are randomly selected through matching (age and sex) to the enrolled 'MRE+ cases' (1:1 ratio). Matched potential control subjects will then be sent an invitation letter, PIS and reply slip (study interest form with a stamped-addressed envelope for returns) by the gastroenterology team to attend the rheumatology SpA research clinic to be assessed by [name] for clinical evidence of axSpA. CD subjects with a known diagnosis of SpA who are already under review by rheumatology and who have lesions on MRE consistent with axSpA will also be invited to attend this clinic for review outside of their routine NHS care but will be considered as cases. Informed consent for study participation in the SpA research clinic will be performed at the start of the consultation. The same clinical assessments, blood and stool samples and dedicated axial MRI scan of the spine and sacroiliac joints will be performed in this control group and in the group of CD subjects with a known diagnosis of SpA who are MRE+ as in the other cases, but will be funded by the research grant unless clinically indicated.

Control subjects in whom there is no evidence of axSpA (by ASAS, modified New York or CASPAR classification criteria) will be informed by letter, which will also be copied to the subjects GP and gastroenterology consultant. Control subjects who do have evidence of axSpA will be informed by letter (also copied to GP and gastroenterology consultant) and asked to return to [name] NHS rheumatology SpA clinic for ongoing care. CD subjects who already have a diagnosis of SpA (both in the control group and cases group) and are already under review by a rheumatology team will be informed by letter of the research clinic outcome and will be followed up as planned by their primary rheumatology team. We will also send a copy of the clinic letter to their GP, gastroenterology consultant and named rheumatology consultant to inform them of the clinic findings and to notify them of any outstanding tests/ management plans that may need to be considered at the next clinic review.

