8.1 Power analysis

This study will aim to include all CD cases with MRE imaging since 2015; the estimated sample size is therefore 1100 cases.

To our knowledge, there are no studies comparing the sensitivity and / or specificity of MRE scans with gold standard dedicated MRI for the detection of sacroiliitis. However, there have been some studies comparing CT imaging with MRI and these found MRI to be up to 17% more sensitive for the detection of sacroiliitis than CT [48, 49].

Although MRE is expected to be more sensitive at detecting evidence of sacroiliitis than CT, our power calculation is based on the conservative estimate that MRE will detect at $\geq 60\%$ (sensitivity) of

the cases of sacroiliitis, when compared with the gold standard dedicated axial MRI scan. Therefore with 80% power and a two-tailed alpha of 0.05, it is estimated that ≥ 60 control subjects (MRE normal) will be required for the study. It is estimated that a sample of >60 cases (with abnormal MRE scans) would be needed since the sample size required to assess specificity for a screening test is less than that of sensitivity. Case and controls will be recruited in a ratio of 1:1. From the 1100 MRE scans already performed, it is expected that $\geq 90\%$ will have a diagnosis of CD, i.e. 990 subjects. We estimate that $\geq 50\%$ of postally invited participants will consent to participate in the study, giving approximately 445 MRE scans for review.

The two previous studies assessing IBD patients for evidence of sacroiliitis using MRE imaging estimated the prevalence to be 16.7% and 15% [27, 28]. We therefore estimate to recruit ≥ 66 subjects with positive MRE scans (cases) and ≥ 66 matched controls. This is a conservative estimate, greater than the minimum number needed to recruit.

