Appendix 7: Classification Criteria for Psoriatic Arthritis (CASPAR) [23].

To meet the CASPAR (CIAssification criteria for Psoriatic ARthritis) criteria, a patient must have inflammatory articular disease (joint, spine, or enthesal) plus ≥ 3 points from the following 5 categories:

1. Evidence of current psoriasis, a personal history of psoriasis, or a family history of psoriasis.

Current psoriasis is defined as psoriatic skin or scalp disease present today as judged by a rheumatologist or dermatologist.

† A personal history of psoriasis is defined as a history of psoriasis that may be obtained from a patient, family physician, dermatologist, rheumatologist, or other qualified health care provider.

A family history of psoriasis is defined as a history of psoriasis in a first- or second-degree relative according to patient report.

2. Typical psoriatic nail dystrophy including onycholysis, pitting, and hyperkeratosis observed on current physical examination.

3. A negative test result for the presence of rheumatoid factor by any method except latex but preferably by enzyme-linked immunosorbent assay or nephelometry, according to the local laboratory reference range.

4. Either current dactylitis, defined as swelling of an entire digit, or a history of dactylitis recorded by a rheumatologist.

5. Radiographic evidence of juxtaarticular new bone formation, appearing as ill-defined ossification near joint margins (but excluding osteophyte formation) on plain radiographs of the hand or foot.

(The CASPAR criteria have specificity of 98.7% and sensitivity of 91.4%)

(† Current psoriasis is assigned a score of 2; all other features are assigned a score of 1.)

Appendix 8: The spondyloarthritis research consortium of Canada (SPARCC): Magnetic Resonance Imaging index for scoring inflammation in the spine[43].

SCORING METHODOLOGY

1. All scores are dichotomous – present or absent.
2. After scanning the entire spine, 6 discovertebral levels are selected for scoring. These levels are chosen as representing the 6 most abnormal levels on the STIR sequence. Levels scored at a second time point are the same as those on the first.
3. After selecting levels, three consecutive sagittal slices are chosen for scoring at each level representing the most abnormal slices for that level.
4. Only abnormalities on the STIR sequence are scored. T1 SE images are included for anatomical reference.

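### Meeting CASPAR counts as clinical evidence of axSpA without any axial requirement, so peripheral-only psoriatic arthritis can become reference-positive under some readings of an undefined gold standard

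*Combined protocol and SAP*

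**What the plan says.** Cases are assessed for clinical evidence of axSpA "using the 2009 ASAS criteria for axSpA, modified New York criteria for AS and CASPAR criteria for PsA" (section 4.3.1). Controls receive the same assessments, and section 4.3.2 describes those who are cleared as having "no evidence of axSpA (by ASAS, modified New York or CASPAR classification criteria"). Read literally, this is an either-or rule: fulfilling any one of the three sets is evidence of axSpA.

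Appendix 7 states the entry condition for CASPAR: "a patient must have inflammatory articular disease (joint, spine, or enthesal"), plus at least 3 points. Spinal disease is one of three ways in and is not required. Section 2.1 says: "It is estimated that up to 40% of patients with PsA also have axial disease (PsSpA").

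The reference standard appears in two forms. The aim has it as "using dedicated axial magnetic resonance imaging (MRI) with clinical assessment as the gold standard" (section 1.2, repeated in substance in section 3.1). The sample-size argument in section 8.1 speaks of "the cases of sacroiliitis, when compared with the gold standard dedicated axial MRI scan", with no clinical component. Section 4.3.3 compares MRE scores with dedicated MRI scores and says that sensitivity, specificity and AUC will also be determined, without defining a positive reference result. Section 8.2 does not define one either.

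**The concern.** The index test is read at the sacroiliac joints only (section 4.2.1), so it cannot detect arthritis of peripheral joints or peripheral enthesitis. If such disease is labelled axSpA in the reference, an MRE-negative subject who has it is scored as a false negative, although MRE missed nothing that it could have seen. Sensitivity is a headline result of the study, and the number of reference-positive controls is likely to be small, so a few mislabelled subjects matter.

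The same undefined label is used elsewhere in section 8.2: in the percentage of MRE-positive subjects who fulfil criteria for axSpA, and in the regressions on presence of axSpA. Peripheral-only PsA could enter both. Appendix 7 awards points for psoriasis and nail dystrophy, so if these are among the extra-articular features studied under objective 4, part of that association would be built into the label.

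**Working it through.** **1. The plan's own figures.** Section 8.1 takes 990 subjects, at least 50% consent and about 445 scans. 990 × 0.5 = 495; the figure 445 follows only with a further 0.9 (990 × 0.5 × 0.9 = 445.5). Then 445 × 0.15 = 66.75, which agrees with at least 66 cases and, at 1:1, at least 66 controls. The requirement of at least 60 controls cannot be reproduced, because no null value or precision target is given. Nothing below depends on it.

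**2. Which reference rules let peripheral-only CASPAR in?** Take a subject with peripheral PsA, CASPAR met, ASAS and modified New York not met, and a normal axial MRI.

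| Reading of the gold standard | Status of this subject |
|---|---|
| MRI alone (section 8.1) | negative |
| MRI and clinical criteria both required | negative |
| MRI or clinical criteria | positive |
| Clinical criteria alone | positive |

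The documents do not choose among these rows.

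**3. Size under the last two rows.** Assumptions, none of them in the documents: PPV 60%, NPV 95%, and a share q of 1%, 2% or 5% of subjects without axSpA who meet CASPAR through peripheral disease, equal in MRE-positive and MRE-negative subjects. Then

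Se(q) = [TP + q·FP] / [TP + q·FP + FN + q·TN].

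*Unweighted 1:1 sample, 66 and 66.* TP = 0.60 × 66 = 39.6; FP = 26.4; FN = 0.05 × 66 = 3.3; TN = 62.7.
- q = 0: 39.6/42.9 = 92.3%
- q = 1%: 39.864/43.791 = 91.0%
- q = 2%: 40.128/44.682 = 89.8%
- q = 5%: 40.92/47.355 = 86.4%

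*Weighted back to 445 screened, 67 positive and 378 negative.* TP = 40.2; FP = 26.8; FN = 18.9; TN = 359.1.
- q = 0: 40.2/59.1 = 68.0%
- q = 1%: 40.468/62.959 = 64.3%
- q = 2%: 40.736/66.818 = 61.0%
- q = 5%: 41.54/78.395 = 53.0%

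The weighted loss is larger because each sampled control stands for about 378/66 = 5.7 MRE-negative subjects. With NPV 90%, the weighted figures are 51.5% falling to 49.6%, 47.7% or 43.1%.

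*Started at the plan's 60% sensitivity* (66 positive, 379 negative, PPV 60%, so TP = 39.6 and FN = 26.4), the weighted figures are about 57%, 55% or 48%. With PPV between 40% and 80% they span 56–58%, 52–56% and 44–51%.

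**4. Direction.** MRE-positive subjects with peripheral-only CASPAR become true positives and push sensitivity up. The net effect is downward when MRE positivity among the relabelled subjects is below the true sensitivity. Under the weighted assumptions at q = 1%, that positivity is 0.268/(0.268 + 3.591) = 6.9%, against 68%. Specificity does not move when q is equal in both groups, because TN and FP are both multiplied by (1 − q).

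**5. The percentage of MRE-positives fulfilling criteria.** If CASPAR counts, 39.6/66 = 60.0% becomes 60.4%, 60.8% or 62.0%. This effect is small and upward.

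**The case against.** The strongest reply is that the control sentence in section 4.3.2 is about result letters and return to clinic, not about the accuracy analysis. Section 4.3.1 labels CASPAR as criteria for PsA, and objective 2 names the three sets individually. MRI with clinical assessment can naturally be read as requiring both, and section 8.1 uses MRI alone; under either, sensitivity is untouched. This stands. A reader might infer that the plan makes peripheral PsA reference-positive and so will understate sensitivity. The documents do not support that, because no section adopts the rule that would produce it.

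Two further replies concern size. First, section 8.2 specifies no weighting, so the fall from 68% to 53% belongs to an analysis that the plan does not describe; on the unweighted sample the largest drop shown is about 6 points. Second, CASPAR is not easily met from the scheduled data. The listed tests include neither rheumatoid factor nor hand or foot radiographs. Unless these are already on record, a subject needs current psoriasis (2 points) plus nail disease or dactylitis, or a personal or family history plus both. The higher values of q are therefore doubtful. At 1% to 2%, about one control is affected (0.01 × 62.7 = 0.6; 0.02 × 62.7 = 1.3). Both replies limit the size.

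They do not remove the textual defect. The only written criterion for clinical evidence of axSpA admits CASPAR with no axial restriction, and nothing in sections 4.3.3 or 8.2 stops an analyst from applying it.

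**Conclusion.** The point holds conditionally. The plan names a classification that peripheral disease can satisfy as evidence of axial disease, and it leaves open how that evidence enters the gold standard. Under MRI alone, or MRI and criteria together, sensitivity is unaffected. Under an either-or or clinical-only rule, a fall is probable but not certain: on the main assumptions, about 1 to 6 points unweighted, or 4 to 15 points if weighted to the screened cohort. PPV, NPV and the frequency of peripheral-only CASPAR are assumptions, so these are ranges and not predictions. The 40% figure in section 2.1 describes PsA generally, not PsA within this Crohn's cohort; it shows that non-axial PsA is common, not how often it will occur here.

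It would go too far to say that the study's sensitivity is biased as planned. The correction should still be made: it is cheap, and it also settles the axSpA label used in the section 8.2 percentage and regressions, which matters even if the accuracy reference turns out to be MRI alone.

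**What to change.** Make the change in section 8.2 only, before reference results are linked to MRE scores:
- Define reference-positive axSpA and state explicitly how the dedicated MRI and the clinical criteria combine.
- Count CASPAR toward axSpA only when the inflammatory articular disease is axial (spine or sacroiliac).
- Analyse peripheral-only CASPAR as PsA without axial disease, reference-negative for axSpA.
- Use the same definition for the percentage fulfilling criteria for axSpA and for the regressions on presence of axSpA.
- Keep the separate CASPAR proportion that objective 2 asks for.

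Sections 1.2 and 3.1, 4.3.1, 4.3.2, 8.1 and Appendix 7 must be reconciled with that definition for analysis purposes. The letter and recall arrangements in section 4.3.2 concern clinical care and are left unchanged by this proposal.

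The cost is wording plus one axial/peripheral field on the form. History, joint counts, enthesitis index and axial MRI are already collected (sections 4.3.1 to 4.3.3). Slightly fewer subjects would carry the axSpA label.

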4.3.3 Axial MRI Scan

Non-contrast MRI imaging of the whole spine and sacroiliac joints, using a dedicated protocol including T1 weighted and fluid sensitive sequences, will be performed in both the cases and controls. Images will be reviewed by two independent expert musculoskeletal radiologists ([name] and a colleague musculoskeletal radiologist) and any discrepancies will be decided by consensus agreement. Since MRI review by a second radiologist is not standard of care, it is funded by the research grant for the clinically indicated axial MRI scans. The MRI review by both of the radiologists for the axial MRI scans performed for research purposes is funded by the research grant.

These will be assessed and scored using the spondyloarthritis research consortium of Canada (SPARCC) MRI index criteria which is a validated scoring system for the assessment of spinal and sacroiliac joint inflammation on MRI [43, 44]. To calculate the SPARCC MRI index criteria score for the spine, the six most abnormal discvertebral levels on the STIR sequence are used. At each of the 6 levels, 3 consecutive slices are included and each slice is divided into four quadrants with each quadrant being scored as normal (score 0) or increased signal (score 1). In addition, each slice is scored for intensity and depth of inflammation to give a total possible score of 108 (see Appendix 8). To calculate the SPARCC MRI index criteria score for the sacroiliac joints, six coronal slices of the

sacroiliac joints on the STIR sequence are chosen and each slice is divided into four quadrants. Each quadrant is then scored as normal (score 0) or increased signal (score 1). In addition, each slice is scored for intensity and depth of inflammation to give a total possible score of 72 (see Appendix 9). The SPARCC MRI index criteria has been validated and reported to be the most reliable MRI inflammation scoring system in a number of studies due to its sensitivity to changes and high inter-reader reliability [45-47]. The dedicated MRI scans will also be scored using the specifically designed scoring system as follows:

- i) Joint margins and contour (score range 0 – 2; 0=normal, 1=mildly abnormal, 2=severely abnormal)
- ii) Juxta-articular bone marrow signal (0 – 3; 0=normal, 1=mild, 2=moderate, 3=severe)

The SPARCC MRI index criteria score will then be used to determine the validity of our specifically designed scoring system for the dedicated axial MRI scans. The scores of the dedicated MRI scans will then be compared to the MRE scores for each patient to determine the validity of using MRE as a screening tool for axSpA in patients with CD. The sensitivity, specificity and area under the ROC curve of using MRE as a screening tool will also be determined.

If an unexpected finding is identified, such as a fracture or potential malignancy, then the gastroenterology team will be informed and appropriate onward referrals and communication (in-person or telephone, as deemed clinically appropriate) to the patient will be made.

5. Study subject selection

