4.2 ProSpA-CD-Screen phase

4.2.1 MRE review

The MRE scans at CUH are typically performed using both an oral contrast agent and intravenous Gadolinium to diagnose and assess the extent of CD. The images also capture the lower thoracic spine/ thoracolumbar junction and lumbar spine in the coronal plane and sacroiliac joints in coronal and axial planes. It is the coronal and axial images of the sacroiliac joints that we will be using to assess for evidence of axSpA (sacroiliitis). There are a number of different sequences included for the MRE scans at Addenbrookes hospital including the SSFSE FS (single shot fast spin echo fat suppressed) and LAVA FLEX sequences which are fat suppressed (the complete list of MRE sequences used can be found in Appendix 4).

For the subjects who consented to have their MRE imaging reviewed, two trained scorers (one musculoskeletal radiologist, [name]; one rheumatologist, [name]) will assess MRE imaging (sacroiliac joints) for evidence of axSpA using a specifically designed scoring system (see below). The MRE assessors will be blinded to the subjects co-morbidities (other than CD). Training sessions for this will be delivered by a consultant musculoskeletal radiologist ([name]). This scoring system was developed by an expert musculoskeletal radiologist ([name]) for this study to specifically identify features of sacroiliitis on both MRE and dedicated MRI spine images, and should permit reliable intergroup comparisons. It has not yet been used in clinical practice due to a lack of previous research on this topic. Scores will be compared and discrepancies decided by consensus. If the two assessors ([name]) are unable to reach a consensus for a particular subject, [name] (considered the 'gold-standard' scorer) will be asked to review and score the images. [name] will be one of the two expert consultant musculoskeletal radiologists who will be reviewing and scoring the subsequent dedicated axial MRI scans and therefore to prevent any scoring bias, the MRE images reviewed by [name] in the ProSpA-CD-Screen phase will be anonymised (patient identifiable data removed). The site of CD involvement in the gut will also be reviewed and documented, for further analysis.

Training will also be provided to identify significant sacral fractures and significant infiltrative bone lesions. If an unexpected finding of this sort should arise, the imaging will be reviewed by the

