7.1 General

All information collected during the course of the study will be kept strictly confidential.

Each subject will be assigned a unique subject study identification code which will be linked to their hospital number on a secure password protected electronic Microsoft-Access database and stored on the Cambridge University Hospitals NHS Foundation Trust (CUH NHSFT) computer network.

The clinic encounter for the cases in the NHS SpA clinic will be documented on to the CUH NHSFT electronic health record system (Epic) and a letter will be sent out to the patient, their GP and gastroenterology consultant to summarise this encounter. The clinic encounter for the controls and CD subjects with a known diagnosis of SpA in the SpA research clinic will also be documented on the Epic system and a letter will be generated from this clinic to the subject, GP, gastroenterology consultant and rheumatology consultant if appropriate. For the cases in the NHS SpA clinic, the PROMs will be labeled with the patient's details (name, date of birth and hospital number) as this will

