be part of their standard NHS care. PROMs for the control group and group of CD subjects with a known diagnosis of SpA in the SpA research clinic will be labeled with the subjects unique study identification code only as this will be outside of their routine NHS care. The blood tests (FBC, renal function, LFTs, CRP, ESR, HLA B27), stool sample for faecal calprotectin and dedicated axial MRI scan of the spine and sacroiliac joints for all subjects within the study will be labeled as per standard trust policy with subject details (name, date of birth, hospital number) and will be requested, reported and stored on the Epic system. Where these tests are performed for research purposes and not standard of care, we will receive written consent from the subject for this. The extra blood and stool samples taken for storage and future analysis for all subjects will be labeled with the unique subject study identification code only. When the subject data is transcribed on to the secure password protected electronic Microsoft-Access database (for all subjects in the study) it will be assigned to the appropriate unique subject study identification code which will be linked to the subject's hospital number. All other identifiable data (such as name, date of birth and NHS ID number) will be removed. This will only be accessible to the investigator team. [name] is the 'Data Protection Officer' for CUH NHSFT.

Cambridge University Hospitals NHSFT will comply with all aspects of the Data Protection Act 1998 and operationally this will include:

- 7.1.1 Consent from subject to record personal details including name, date of birth, address and telephone number, NHS identification number, hospital identification number, GP name and address.
- 7.1.2 Appropriate storage, restricted access and disposal arrangements for the subjects personal and clinical details.
- 7.1.3 Consent from subject for access to their medical records by responsible individuals from the research staff, the sponsor or from regulatory authorities, where it is relevant to study participation.
- 7.1.4. Consent from subject for the data collected for the study to be used to evaluate safety and develop new research.

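### Section 4.3.3 does not mask the two axial-MRI readers to MRE result or case/control group, so the reference read is open to review bias

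*Combined protocol and SAP*

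**What the plan says.** **Axial-MRI read.** Section 4.3.3: "Images will be reviewed by two independent expert musculoskeletal radiologists". Discrepancies go to consensus. The scans are scored with SPARCC and with the study-specific score. For clinically indicated scans, only the second radiologist's review is charged to the grant, because a second review is not part of standard care.

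**Identification of the scans.** Section 7.1 says that the axial MRIs of all subjects "will be labeled as per standard trust policy with subject details (name, date of birth, hospital number"). On where these scans are handled, the same sentence goes on: "and will be requested, reported and stored on the Epic system". On the clinic visits it says: "The clinic encounter for the cases in the NHS SpA clinic will be documented on to the CUH NHSFT electronic health record system". The encounters of controls and of subjects with known SpA "in the SpA research clinic will also be documented on the Epic system".

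**Existing safeguards.** Section 4.2.1 blinds the MRE assessors to co-morbidities other than Crohn's disease, and section 5.2.1.1 identifies those assessors as two specialist registrars. If they "are unable to reach a consensus for a particular subject", an adjudicator scores the MRE. That adjudicator "will be one of the two expert consultant musculoskeletal radiologists who will be reviewing and scoring the subsequent dedicated axial MRI scans". To prevent scoring bias, the MREs this person reviews "in the ProSpA-CD-Screen phase will be anonymised (patient identifiable data removed").

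**Use of the scores.** Section 4.3.3 compares axial-MRI scores with MRE scores patient by patient, and section 8.1 takes the dedicated axial MRI as gold standard for the sample size.

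**The concern.** In a diagnostic accuracy study, the reference standard should be read without knowledge of the index test. Here the index test defines the groups, since MRE-positive subjects are cases and MRE-negative subjects are controls, so a reader who learns the group has learned the MRE result.

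The axial-MRI read carries much of the reference standard for the main aim, and it leaves room for judgement. The study-specific score grades margins and marrow signal as normal, mild, moderate or severe, and section 4.2.1 states that it has not yet been used in practice. SPARCC is more structured but still needs a decision on signal, intensity and depth. If borderline scans are resolved toward the MRE result, the two modalities will agree more often than they should. An unmasked read cannot be made masked by later analysis, so the point has to be settled before scoring starts.

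**Working it through.** The plan gives no figure to reproduce on this point. The check has two parts: what the text masks, and which way an unmasked read would push the results.

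**1. Every statement on masking, set side by side**

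| Place | Who is masked | To what |
|---|---|---|
| 4.2.1, MRE assessors | the two registrars | co-morbidities other than Crohn's disease |
| 4.2.1, adjudicated MREs | one of the two axial-MRI readers | identity of the MRE, when the registrars cannot agree |
| 4.3.3, axial-MRI readers | none stated | none stated; described as independent |
| Appendices 8 and 9 | SPARCC observer | time sequence only |

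Calling the readers independent describes the readers. It does not say what information they are given. No row masks either axial-MRI reader, at the axial-MRI read, to MRE result or group.

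**2. How group could become known.** Under section 7.1 the scan carries name, date of birth and hospital number, and its request sits on the same system as the clinic encounter. For subjects without known SpA, the type of clinic gives the group away: MRE-positive subjects attend the NHS clinic (4.3.1) and MRE-negative subjects the research clinic (4.3.2). For known-SpA subjects it does not, because both groups attend the research clinic. For clinically indicated scans, the funding text in 4.3.3 implies that the first of the two reads is the ordinary standard-of-care read, which would be made with identifiers and request in view.

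**3. Direction.** Let a = MRE+ and reference+, b = MRE+ and reference−, c = MRE− and reference+, d = MRE− and reference−.

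- Sensitivity = a/(a+c); specificity = d/(b+d).
- A reference read moved toward the MRE result goes from b to a, or from c to d.
- Moving b to a raises a and lowers b. Moving c to d lowers c and raises d. Each move raises both sensitivity and specificity.

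**4. Illustration only, on assumed inputs.** Take 66 MRE+ and 66 MRE− (section 8.1), sensitivity 60% (section 8.1, here applied directly to the 1:1 sample), and an assumed a = 33. Then b = 33, c = 33 × 0.4/0.6 = 22, d = 44, and specificity = 44/77 = 57.1%. Let a share f of the discordant reads (b and c) move toward the MRE result.

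| f (assumed) | Sensitivity | Specificity |
|---|---|---|
| 0 | 33/55 = 60.0% | 44/77 = 57.1% |
| 5% | 34.65/55.55 = 62.4% | 45.1/76.45 = 59.0% |
| 10% | 36.3/56.1 = 64.7% | 46.2/75.9 = 60.9% |
| 20% | 39.6/57.2 = 69.2% | 48.4/74.8 = 64.7% |

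With a = 20 or a = 45 instead, a 20% shift takes sensitivity from 60.0% to 73.2% or 67.2%, and specificity from 53.4% to 60.1% or from 63.2% to 71.4%. The documents give neither f nor a, so the table shows how the mechanism works and is not an estimate of bias in this study.

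**The case against.** The best defence is that the plan already keeps the two reads largely apart. Registrars score the MREs and consultants read the axial MRIs. The one planned overlap in scoring is the adjudicator, and every MRE that person scores is anonymised, so within that pathway the safeguard covers the whole overlap. Section 7.1 is about data handling and does not say how images are presented for study scoring. No passage puts the MRE study score on Epic, and transcribed study data go into a password-protected database under the study code. Two readers with consensus and quadrant-level scoring also limit the room for drift.

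Most of this stands and lowers the risk. It does not close the gap. The safeguards act on the MRE side and leave the axial scan identifiable, with group open to inference from the clinic route. Consensus does not remove a bias that both readers share.

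Three stronger readings are tempting, and the documents do not support them:

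- **That the reference read is biased.** The plan does not say that readers will consult the record, and masking may be arranged in practice without being written down.
- **That access to clinical findings in itself inflates both accuracy measures.** Clinical assessment is part of the declared gold standard (sections 1.2 and 3.1), and no such effect is shown. Clinic details matter here because they can reveal the group.
- **That the clinical assessor's knowledge of MRE status is a design error.** It follows from the referral route, and applies only to subjects without known SpA.

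**Conclusion.** The point holds as a gap in the design of the reference read. As written, the workflow leaves both axial-MRI readers able to learn MRE status, and nothing in the plan says that they will be kept from it. The probable effect is to raise both sensitivity and specificity, assuming that a reader who knows the MRE result would tend to settle borderline scans toward it. The presence and size of the effect cannot be derived, because the documents give no rate of borderline reads and no rate of shift. It should be put right before the axial MRIs are scored, because it concerns the main aim and a better procedure is available at small cost. If masking is already intended, writing it into section 4.3.3 settles the matter.

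**What to change.** Add to section 4.3.3:

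*For study scoring (SPARCC and the study-specific score), the two radiologists read the axial MRIs under the study code, with cases and controls in mixed order and with identity, request text, clinic details and MRE result withheld. Scores, including consensus scores, are locked before linkage to MRE. The clinical report is kept separate from the study score.*

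Also state the order of reads. Where a study reader would also issue the clinical report, the masked score is recorded first. Alternatively, where routine service allows, a radiologist who is not a study reader issues the report. A masked score made after the clinical read would not be masked.

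Report as a limitation that, for subjects without known SpA, the clinic route reveals MRE status to the clinical assessor.

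**Cost.** No extra scan and no new reader for the study scoring. The work is coded export of about 66 + 66 = 132 scans (section 8.1 plans at least 66 per group), and possibly a second look by the same reader at some clinically indicated scans; the number of these is not given. Section 12 budgets consultant time for two reviews of the axial scans, but it is unclear whether that covers a separate masked score, so the sponsor should confirm it.
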